## Protocol Synopsis of Study TNP-2092-06

**Title of study:** A Phase 1b/2a, single-center, randomized, double-blind, placebo-controlled study to evaluate the safety, tolerability, pharmacokinetic characteristics, and preliminary efficacy of multiple ascending doses of TNP-2092 Capsules in liver cirrhosis patients with hyperammonemia

**Protocol No.:** TNP-2092-06

**Sponsor:** TenNor Therapeutics (Suzhou) Limited.

**Investigator:** [name], The First Hospital of Jilin University

**Study center:** The study was conducted in a single center in China.

**Study Phase:** 1b/2a

### Objectives

Primary objectives:

1. To evaluate the safety and tolerability of TNP-2092 Capsules in liver cirrhosis patients with hyperammonemia.
2. To evaluate the pharmacokinetic characteristics of TNP-2092 Capsules in liver cirrhosis patients with hyperammonemia.

Secondary objectives:

1. To evaluate the preliminary efficacy of TNP-2092 Capsules in liver cirrhosis patients with hyperammonemia.
2. To observe the effects of TNP-2092 Capsules on hepatic encephalopathy related clinical symptoms and signs, neuropsychological indicators, and quality of life in liver cirrhosis patients with hyperammonemia.

### Investigational Product:

**TNP-2092 Capsules:** strength 100 mg, Storage condition: stored in a cold place (2-10 °C), sealed, and protected from light.

**TNP-2092 Placebo Capsules:** strength: NA. Storage condition: stored in a cold place (2-10 °C), sealed, and protected from light.

### Study Design

The aim of this study is to evaluate the safety, tolerability, and pharmacokinetic characteristics of TNP-2092 Capsules in liver cirrhosis patients with hyperammonemia; and to preliminarily observe the effects of the study drug on blood ammonia and hepatic encephalopathy related clinical symptoms and signs, neuropsychological indicators, and quality of life in liver cirrhosis patients with hyperammonemia.

A total of 3 dose groups will be set up, i.e., 100 mg BID, 300 mg BID and 600 mg BID groups. Drugs will be orally administered 30 min after breakfast and dinner for 14 consecutive days, and last dose will be administered 30 min after breakfast on the morning of D15. Each dose group will include a study drug TNP-2092 capsule arm and a placebo control arm. Subjects will exit upon completion of the safety and tolerability evaluation on D17.

Twelve liver cirrhosis patients with hyperammonemia are planned to be enrolled in each dose group. The 12 patients will be assigned in a ratio of 2:1 to the TNP-2092 capsule arm and the placebo arm, with 8 patients receiving TNP-2092 Capsules and 4 receiving placebo.

In each dose group, a sentinel-based sequential enrollment design will be applied, and the 12 patients will be sequentially enrolled into two subgroups which will consist of 3 and 9 patients

respectively. If the drug is evaluated as tolerable in the safety and tolerability assessment on D2, D4 and D7 of treatment in the first subgroup, enrollment for the next subgroup may start.

Enrollment for the second dose group may start only after the previous dose group has fully completed the treatment period and passed the safety and tolerability evaluation.

During the study, safety and tolerability will be observed and evaluated in subjects at scheduled time points in the protocol. PK blood samples will be collected from subjects at scheduled time points in the protocol for pharmacokinetic analysis.

### **Dosing Regimen**

The drug is administered orally 30 min after the breakfast and dinner in the treatment period (Days 1-14), and the last dose is administered 30 min after the breakfast on Day 15. Water are not allowed from 1 hour pre-dose to 2 hours post-dose on Day 1 and Day 15.

### **Screening Evaluations**

After signing the written Informed Consent Form, subjects received a series of examinations, including: demographic data (including sex, ethnicity, age, fertility status, weight, height, and BMI), clinical assessment of HE grade, asterixis examination, neuropsychological evaluation, medical history, surgical history, smoking history, alcohol/diet, previous medication, physical examination, vital signs (blood pressure, pulse and body temperature), 12-lead ECG, chest X-ray, abdominal B ultrasound (liver, bile, pancreas and spleen), Fibroscan (transient elastography), clinical laboratory tests (blood ammonia, hematology, blood chemistry, urinalysis, stool routine, coagulation), infectious disease tests (hepatitis B serologic test, hepatitis C antibody, hepatitis C core antigen, HIV antigen/antibody, treponema pallidum antibody, additional RPR test should be performed for those tested positive in treponema pallidum antibody), blood pregnancy test (for females only), to confirm the inclusion criteria and exclusion criteria.

### **Admission (Baseline) Evaluations**

Admission (baseline) will be occurred on D-1.

Baseline evaluations: Medical history, surgical history, clinical laboratory tests, physical examination, vital signs, 12-lead ECG, serum pregnancy test (females only), urine drug screen, alcohol breath test, fasting blood ammonia concentration, asterixis, Neuropsychological evaluation: Number connection test (NCT-A) and Digit symbol test (DST), Quality of life score (quality of life scale for patients with mild hepatic encephalopathy).

Note: Screening results are valid within 7 days for clinical laboratory tests

### **Diagnosis and main criteria for inclusion**

Each subject was required to meet all of the following criteria to be eligible for study enrollment:

- 1) 18-65 (inclusive) years of age, male or female.
- 2) Clinically diagnosed with liver cirrhosis.
- 3) Fasting venous blood ammonia above upper limit of normal (ULN).
- 4) Organ functions must meet the following criteria:
  - a) Peripheral blood: absolute neutrophil count  $\geq 0.5 \times 10^9/L$ , platelet  $\geq 20 \times 10^9/L$ , hemoglobin  $\geq 8$  g/dL.
  - b) Liver: aspartate aminotransferase (AST) and alanine aminotransferase (ALT)  $\leq 5 \times$  ULN; serum total bilirubin (TBL)  $\leq 5 \times$  ULN.
  - c) Kidney: creatinine clearance  $\geq 60$  mL/min.
  - d) No malabsorption or other gastrointestinal disorders that affect drug absorption.
- 5) Weight  $\geq 45$  kg and body mass index [BMI = weight (kg)/height (m^2) ] between 18 and 34 (inclusive) kg/m^2.
- 6) Subjects (including their partners) will have no pregnancy plan and voluntarily take effective contraceptive measures within 6 months after drug withdrawal. Refer to Appendix 9 for specific contraceptive measures.

- 7) Subjects or their legal representatives sign the Informed Consent Form and fully understand the content, procedures, and potential adverse reactions prior to the initiation of the study.
- 8) Able to complete the study per the requirements in the study protocol.

Subjects meeting any of the following criteria were ineligible for study enrollment:

- 1) Subjects who are allergic to rifamycin or quinolone antibacterial agents or those with an allergic constitution.
- 2) Pregnant or lactating women, or women of childbearing age with a positive pregnancy test from the screening period to initiation of the study treatment.
- 3) Subjects with serious nervous or mental disorders.
- 4) Subjects with Child-Pugh class C liver cirrhosis.
- 5) Subjects with Grade 2 or above hepatic encephalopathy.
- 6) Subjects who have been diagnosed with *Clostridium difficile*-induced pseudomembranous enteritis within 3 months.
- 7) Subjects who have had systemic infection or gastrointestinal bleeding within 7 days prior to screening.
- 8) Subjects with clinically significant abnormal clinical laboratory tests or other clinical findings indicative of clinically significant disorders that, in the opinion of the investigator, make them not eligible for this clinical study.
- 9) Subjects who have used sedatives, probiotics, cathartics or antibacterial agents within 7 days prior to screening.
- 10) Subjects who have used other study drugs or participated in other drug clinical trials within 1 month prior to screening.
- 11) Subjects need to use the following concomitant drugs during the study treatment period: cathartics and drugs for ammonia reduction listed in 5.2.1 in the Guidelines on the Management of Hepatic Encephalopathy in Liver Cirrhosis 2018 (e.g., lactulose, lactitol, LOLA, rifaximin, other antibacterial agents, etc.) ; HIV protease inhibitors (e.g., ritonavir boosted or non-boosted saquinavir, atazanavir, darunavir, fosamprenavir, tipranavir, etc.) ; praziquantel; halothane; class IA and III antiarrhythmics (disopyramide, procainamide, quinidine, amiodarone, dofetilide, dronedarone, ibutilide, sotalol, etc.) ; strong inhibitors and inducers of liver metabolic enzymes;
- 12) Positive HIV antigen/antibody screen; positive *Treponema pallidum* antibody screen requires the investigator's judgment with the consideration of RPR results.
- 13) Positive urine drug screen or history of drug abuse within the past 5 years.
- 14) Positive alcohol breath test.
- 15) Acute diseases or concomitant medications from screening to study medication.
- 16) Other circumstances deemed by the investigator to be unsuitable for enrollment in this study.

#### **Safety and Tolerability Evaluation**

All participants are observed for any adverse events occurring during the clinical study, and their clinical manifestations, severity, onset time, end time, treatment measures and outcome are recorded, and their correlation with the investigational product shall be determined.

Safety and tolerability evaluation includes adverse events (AE), clinical laboratory tests (hematology, blood biochemistry, coagulation, urinalysis), vital signs (blood pressure, pulse rate, respiratory rate, and body temperature), 12-lead electrocardiogram (ECG) and physical examination.

**Pharmacokinetics Sample Collection Time Point:**

- Day 1: 30-60 min prior to the first dose, and 0.5 h, 1 h, 2 h, 3 h, 4 h, 5 h, 6 h, 8 h, 10 h and 12 h post-dose (prior to the next dose).
- Days 3, 5, 7, 9, 11 and 13: 30-60 min prior to the first dose.
- Day 15: 30-60 min pre-dose, and 0.5 h, 1 h, 2 h, 3 h, 4 h, 5 h, 6 h, 8 h, 10 h, 12 h, 24 h and 36 h post-dose.

**Efficacy Evaluation**

Fasting venous blood ammonia concentration and area under the blood ammonia concentration-time curve. Asterixis: elicited (yes/no). Neuropsychological evaluation: Number connection test (NCT-A) and Digit symbol test (DST). Quality of life score (quality of life scale for patients with mild hepatic encephalopathy). Clinical grade of hepatic encephalopathy (HE).

**Statistical methods**

SAS 9.4 was used for the statistical analysis.

Population for analyses were:

- Full Analysis Set (FAS): all the subjects who were randomized into groups.
- Safety Analysis Set (SS): all the subjects who have been randomized into groups and received at least one dose of study drug.
- PK Concentration Analysis Set (PKCS): all the subjects who have been randomized into groups, received at least one dose of study drug, and have at least one evaluable blood drug concentration.
- PK Parameter Analysis Set (PKPS): all subjects who have been randomized into groups, have received at least one dose of study drug, and have at least one evaluable pharmacokinetic parameter.

**Interim analysis:**

No interim analysis was planned.

**Efficacy analysis:**

All efficacy endpoints will be descriptively summarized. Changes at each post-baseline visit from baseline will be calculated for all endpoints except asterixis.

For fasting blood ammonia concentration, if data follow a normal distribution, single-group t-test will be used to determine, by treatment group, whether the change from baseline at each post-baseline time point is 0; and analysis of covariance will be performed for differences between treatment groups and between each treatment group and the control group in changes from baseline at each post-baseline time point. If data do not follow a normal distribution, Wilcoxon signed rank test and Wilcoxon rank sum test will be used. The areas under the blood ammonia concentration-time curve will be calculated, and t-test or Wilcoxon rank sum test will be used for inter-group comparison. Normal fasting venous blood ammonia concentrations across all post-baseline visits in each dose group and the placebo group will be counted, and their percentages in all measurements will be calculated; Logistic regression will be used to compare the difference in the percentage of normal blood ammonia concentrations between each dose group and the placebo group.

With regard to whether asterixis is elicited, baseline, D7 and D15 results will be compared by treatment group using paired chi-square test; Logistic regression (with baseline and group as

independent variables) or non-parametric methods will be used for inter-group comparison of D7 and D15 results.

For NCT-A and DST results, t-test or Wilcoxon signed rank test will be used to determine whether the change from baseline in each treatment group is 0 on D7 or D15. Inter-group t-test or Wilcoxon rank sum test will be used to determine whether changes on D7 and D5 are different between treatment groups and between each treatment group and the control group.

NCT-A and DST results will be analyzed using age-corrected scaled scores.

For the quality of life scale for patients with mild hepatic encephalopathy, the total score of the 30 questions will be calculated for the subject, and paired t-test will be used to determine whether the change from baseline at each post-baseline visit is 0 within each group; and analysis of covariance (baseline as the covariate and group as the fixed factor) to determine whether changes from baseline at each post-baseline visit are different between the groups (including the placebo group).

For HE grades, Wilcoxon signed rank test will be used to determine whether changes from baseline in each treatment group are different on D7 or D15. Wilcoxon rank sum test will be used to determine whether changes on D7 and D15 are different between treatment groups and between each treatment group and the control group.

If D7 or D15 data are missing, the last observation carried forward (LOCF) approach will be used for imputation.

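### Fasting ammonia: an undefined normality check can replace ANCOVA (no covariate named) with a rank-sum test on change that does not adjust for baseline

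*Combined protocol and SAP*

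**What the plan says.** All of this is in the Efficacy analysis section under Statistical methods, unless noted.

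- **Trigger.** The ammonia methods apply "if data follow a normal distribution, single-group t-test will be used to determine, by treatment group". No test, significance level, variable (raw value, change or residual) or unit (arm, visit or whole endpoint) is given there or elsewhere in the text supplied.
- **If normal.** "analysis of covariance will be performed for differences between treatment groups and between each treatment group and the control group", on "the control group in changes from baseline at each post-baseline time point". No covariate or factor is listed.
- **If not normal.** "If data do not follow a normal distribution, Wilcoxon signed rank test and Wilcoxon rank sum test will be used".
- **Other endpoints in the same section.** The quality-of-life comparison uses "analysis of covariance (baseline as the covariate and group as the fixed factor") and has no normality switch. The asterixis comparison starts from "Logistic regression (with baseline and group as" independent variables.
- **Numbers (Study Design).** There are three dose groups of 12, each "with 8 patients receiving TNP-2092 Capsules and 4 receiving placebo".
- **Baseline (Admission evaluations).** Fasting ammonia is measured on D-1.
- **Status (Objectives).** Efficacy is a secondary, preliminary objective.

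**The concern.** Two statisticians following this text could run different tests on the same data, and the choice is settled only once the data are in hand. When the check fails, the analysis also loses covariate adjustment for a baseline value that is scheduled for every patient. With 8 patients per dose that is avoidable.

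The sponsor names baseline as a covariate for quality of life and for asterixis, so its absence from the ammonia ANCOVA looks like an omission and not a general style. What is at stake is precision and reproducibility of the ammonia comparison. The primary safety and pharmacokinetic conclusions are not affected.

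**Working it through.** **No figure to reproduce.** The documents give no alpha, power, effect size, SD or sample-size derivation for ammonia. The arithmetic available is 3 × 12 = 36 patients, 3 × 8 = 24 active and 3 × 4 = 12 placebo.

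**Why covariate adjustment matters.** Take equal SD σ at baseline and follow-up and correlation r. The variance of change is 2σ²(1 − r). The residual variance after adjusting for baseline is σ²(1 − r²). The ratio of the second to the first is (1 + r)/2:
- r = 0.3: 0.65
- r = 0.5: 0.75
- r = 0.7: 0.85
- r = 0.9: 0.95

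An analysis of change alone therefore loses most when r is low and little when r is near 1.

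**Simulation inputs.** From the documents: 8 per dose, 12 placebo (pooled, which is an assumption) and entry above ULN. Everything else is assumed:
- two-sided 5% level, Shapiro-Wilk at 5%, exact rank-sum on change
- lognormal ammonia, baseline median 1.5 × ULN truncated at ULN, log-SD 0.4 or 0.6, r = 0.5 or 0.7
- falls of 15/33/45% in the three doses, two correlated visits as an illustration
- 4,000 trials per setting (standard error up to 0.8 points)

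**Power (%) at one visit, skewed data.**

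| log-SD, r, fall | Four-group ANCOVA | Rule, one residual check per visit | Rank-sum alone | Rank ANCOVA | ANCOVA − rule | ANCOVA − rank-sum |
|---|---|---|---|---|---|---|
| 0.4, 0.5, 33% | 67.4 | 59.9 | 45.7 | 67.7 | 7.5 | 21.7 |
| 0.4, 0.7, 45% | 98.2 | 95.9 | 90.3 | 98.4 | 2.3 | 7.9 |
| 0.6, 0.5, 45% | 55.4 | 46.4 | 37.9 | 63.4 | 9.0 | 17.5 |
| 0.6, 0.7, 45% | 72.2 | 65.0 | 56.1 | 79.0 | 7.2 | 16.1 |

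Over all eight combinations with a 33% or 45% fall, rank-sum is 8–24 points below four-group ANCOVA and the per-visit rule 2–9 below. With r = 0.3 the per-visit rule is 6–12 below; with r = 0.9 it is 0–3 below.

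**How much of the gap is baseline adjustment.** Part comes from pooling variance over 36 patients instead of 20. In a 2,000-trial run of the first setting, four-group ANCOVA gave 66.6%, dose-v-placebo ANCOVA 58.0% and rank-sum 43.7%. Pooling accounts for 66.6 − 58.0 = 8.6 points, and 58.0 − 43.7 = 14.3 remain. A 3,000-trial run puts the remainder at about 7–12 points in the four tabulated settings; the 2,000-trial run spans 3–16 over all eight. Rank ANCOVA on the same 20 patients beats rank-sum by 7–22 points.

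**Other readings of the check, skewed data.**
- One residual check per visit fires in 32–64% of trials, and two visits then get different tests in 31–47%.
- One overall check never mixes tests but moves the whole endpoint to rank-sum in 38–89%. That rule is 3–15 points below four-group ANCOVA.
- Per-arm checks put doses on different tests in 26–34%. That rule is 1–5 points below four-group ANCOVA, and 0–3 below if ANCOVA is fitted dose by dose.

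**Normal data.** The per-visit check fires in about 5%, and the rule costs 0–1 point.

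**Type I error, skewed data.**
- No dose active: per-visit rule 5.5%, ANCOVA 5.2%, rank ANCOVA 5.1%.
- Inactive dose beside doses with 33% and 45% falls: four-group ANCOVA 7.5–8.9%, present rule 6.8–7.8%, rank ANCOVA 5.0–6.4%, ANCOVA with HC3 3.3–4.5%, two-group ANCOVA 4.2–5.0%. The excess arises because the active doses have smaller spread and pull the pooled variance down.

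**Outliers.** With 10% of visit values raised by 3 SD, ANCOVA ranges from 0.3 points above the per-visit rule to 7 below (for example 44.6% v 51.6%). Rank ANCOVA ranges from 0.5 below to 5 above.

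**The case against.** The strongest case against runs as follows.

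- **Baseline is already used.** The tests are on change, so a reader who infers that the fallback ignores baseline is mistaken: it is subtracted. Only covariate adjustment is missing. This stands.
- **The largest gap is partly an artefact.** The plan does not specify a four-group model, and 8–24 points mixes baseline adjustment with variance pooling. This stands; about 7–12 is the fairer figure for the test itself, and the loss from the rule is smaller still.
- **Raw-scale ANCOVA is not clean under skew.** With variance pooled over four groups it exceeds 5% for an inactive dose beside active ones, somewhat more than the present rule does. This stands, and the fix has to deal with it.
- **The inputs are assumed.** Skew, correlation, falls and the Shapiro-Wilk test are not in the documents. D7 and D15 are named for other endpoints; the ammonia visits are not listed. This stands, so the figures are illustrations. The gap in the text does not depend on them.
- **The text is a synopsis, both tests are named in advance, and efficacy is preliminary and descriptively summarised.** A fuller document may define the check. This limits the weight of the point but does not remove it.

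A reader might also infer that the switch inflates false positives generally, or that it was left open so that a favourable test could be picked. The first is not borne out with no active dose, and nothing in the documents supports the second.

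**Conclusion.** The point holds in a limited form. The text does not define the check, names no covariate for the ammonia ANCOVA, and falls back to a test that cannot take one.

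If ammonia is skewed, the rule costs between 0–3 and 2–9 power points on the per-arm (dose-by-dose) and per-visit readings, and more (3–15) if one overall check decides the endpoint. If ammonia is roughly normal, almost nothing is lost. These figures rest on assumed distributions, on Shapiro-Wilk at 5% and on 12 pooled placebo patients. The case for change is reproducibility and precision at low cost, not control of type I error. It is a worthwhile improvement to a secondary endpoint.

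**What to change.** 1. Delete the normality-triggered switch for the between-group ammonia comparison.
2. At each post-baseline time point fit ANCOVA of change with treatment group as factor and baseline fasting ammonia as covariate, as for quality of life. State which value is baseline: fasting ammonia is scheduled on D-1, but the Admission section also lets screening laboratory results stand for 7 days.
3. Report every planned contrast, dose v placebo and between doses, with a 95% CI.
4. Use HC3 standard errors, or fit each contrast on its two groups only, so that active doses do not distort the error for an inactive one.
5. Replace the unadjusted rank-sum test with rank ANCOVA (rank of the visit value on rank of baseline and group) as the single pre-specified sensitivity analysis.

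**Cost.** SAP wording and one extra analysis; no new data. HC3 changes power by between 1 point up and 6 down. Two-group fits can cost more (66.6% to 58.0% in the example above), which gives back most of the gain over the present rule, so HC3 is the better default under these assumptions. With heavily outlying values ANCOVA can be up to about 7 points below the present rule; rank ANCOVA covers this, but on normal data it is itself 1–5 points below the rule.

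**Separate clarification.** The plan compares ammonia normalisation "between each dose group and the placebo group"; the SAP should confirm that this means the 12 placebo patients pooled across dose groups.

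### The between-group comparison of ammonia AUC has no baseline term, although D-1 fasting ammonia is collected; adjusting for it would probably gain precision at almost no cost

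*Combined protocol and SAP*

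**What the plan says.** The Efficacy Evaluation section lists two ammonia measures: "Fasting venous blood ammonia concentration and area under the blood ammonia concentration-time curve". The Efficacy analysis section treats them differently.

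- **Fasting concentration:** change from baseline at each time point is compared by ANCOVA if normal, otherwise by rank-sum test. The covariate is not named; baseline is the natural reading.
- **AUC:** "The areas under the blood ammonia concentration-time curve will be calculated, and t-test or Wilcoxon rank sum test will be used for inter-group comparison". No covariate and no baseline correction are mentioned.

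Other endpoints in the same section show that baseline adjustment was in mind. Quality of life uses "analysis of covariance (baseline as the covariate and group as the fixed factor"). Asterixis has a logistic regression that includes baseline, with non-parametric methods as an alternative. For the neuropsychological tests the rule is "Inter-group t-test or Wilcoxon rank sum test will be used to determine whether changes on D7 and D5 are different between treatment groups", so changes are compared without a baseline covariate. (D5 is an evident slip for D15.)

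The covariate exists: the Admission (Baseline) Evaluations on D-1 include "fasting blood ammonia concentration, asterixis, Neuropsychological evaluation: Number connection test (NCT-A) and Digit symbol test (DST), Quality of life score".

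**The concern.** AUC is the one continuous efficacy measure compared with neither a stated change score nor a baseline covariate. A general sentence says "Changes at each post-baseline visit from baseline will be calculated for all endpoints except asterixis", but it concerns changes by visit. It does not define a baseline-corrected AUC, and the D-1 assessments list a single fasting concentration, not a baseline curve.

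With 8 active and 4 placebo patients per dose group, chance imbalance in baseline ammonia can be large, and it passes into the unadjusted AUC difference in proportion to r. Under Study Design, each dose group opens only after the previous one has finished treatment. Comparisons of one dose with another, or with placebo pooled over dose groups, therefore span patients enrolled at different times, and baseline differences there need not be chance alone.

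At stake is how clearly the trial can read an ammonia signal from AUC. The primary safety and PK conclusions are not affected.

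**Working it through.** **Inputs from the documents.** 8 active and 4 placebo per dose group and three dose groups (Study Design), so 3 × 4 = 12 placebo patients if pooled. Pooling is not stated, so both cases are shown. The plan gives no power figure to reproduce.

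**Assumptions, not in the documents.** Two-sided 0.05; a true effect of 1 SD; bivariate normal data with equal variances; r from 0 to 0.9 in enrolled patients. The AUC window is also not given.

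**Variance.** For two groups with N patients in all and a random normal covariate:

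Var(ANCOVA) / Var(unadjusted) = (1 − r²)(N − 3)/(N − 4)

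The factor is 17/16 = 1.0625 for N = 20 and 9/8 = 1.125 for N = 12. Setting the ratio to 1 gives break-even r = √(1/17) = 0.24 and √(1/9) = 0.33. At r = 0.5 the ratio is 0.75 × 1.0625 = 0.80 (N = 20) and 0.75 × 1.125 = 0.84 (N = 12). At r = 0.7 it is 0.51 × 1.0625 = 0.54 and 0.51 × 1.125 = 0.57.

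By expected confidence-interval width the break-even values are 0.25 and 0.36. For one four-group model with a common slope (N = 36) the variance break-even is 0.18.

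**Power for AUC** (simulation, 100,000 trials per cell; type I error 4.9–5.1%):

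| r | 8 v 12: t-test / ANCOVA | 8 v 4: t-test / ANCOVA |
|---|---|---|
| 0 | 54 / 52% | 31 / 28.5% |
| 0.2 | 55 / 54% | 32 / 30% |
| 0.3 | 54 / 56% | 31 / 31% |
| 0.5 | 55 / 64% | 31 / 36% |
| 0.7 | 55 / 80% | 32 / 50% |
| 0.8 | 55 / 91% | 31 / 64% |

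**Restricted entry.** Enrolment requires fasting ammonia above the upper limit of normal, which lowers r. Truncating the baseline distribution, with the effect kept at 1 SD of AUC among those enrolled:

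| Part cut off | r before → after | ANCOVA power, 8 v 12 | ANCOVA power, 8 v 4 |
|---|---|---|---|
| Lowest quarter | 0.5 / 0.7 / 0.8 → 0.39 / 0.58 / 0.70 | 59 / 70 / 80% | 33 / 40 / 49% |
| Lower half | 0.5 / 0.7 / 0.8 → 0.33 / 0.51 / 0.63 | 56 / 64 / 73% | 32 / 37 / 43% |

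The t-test stays at 54–55% and 31–32%.

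**Chance imbalance.** The SD of the baseline difference, in baseline SDs, is √(1/8 + 1/12) = 0.46 for 8 v 12 and √(1/8 + 1/4) = 0.61 for 8 v 4. An imbalance of that size moves the unadjusted AUC difference by 0.46r or 0.61r: at r = 0.5, 0.23 and 0.31 SD; at r = 0.7, 0.32 and 0.43 SD.

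**Skewed data.** With lognormal data and a 1-SD shift on the log scale, rank-sum on AUC against log-scale ANCOVA gives about 51 / 64% (8 v 12) and 29 / 36% (8 v 4) at r = 0.5.

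**Drift between dose groups (illustration).** For 8 v 8 across dose groups with no true difference, assume a 0.5-SD drift in baseline ammonia that acts only through baseline. False-positive rates, t-test / ANCOVA, are 5.9 / 4.9% at r = 0.3, 7.6 / 5.1% at 0.5 and 10.1 / 5.0% at 0.7.

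**NCT-A and DST (secondary).** Against a change score the variance ratio is ((1 + r)/2)(N − 3)/(N − 4): 0.80 and 0.84 at r = 0.5, and 0.90 and 0.96 at r = 0.7 (N = 20 and N = 12). ANCOVA loses above r = 2 × 16/17 − 1 = 0.88 or 2 × 8/9 − 1 = 0.78. Power, change t-test / ANCOVA, for 8 v 4 is 31 / 36% at r = 0.5, 48 / 50% at 0.7 and 91 / 88% at 0.9.

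**The case against.** The planned test is valid within a dose group, efficacy is preliminary, the supplied text sets no power target, and fasting ammonia already has an ANCOVA at each time point. On that view this is a preference. Validity and the secondary status stand, and they are why the point is minor. They are not a reason to leave an available covariate unused in groups of 8 and 4.

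A second argument is that the AUC might be baseline-corrected, since subtracting baseline times duration needs only the D-1 value. The text supplied is a synopsis and does not define the AUC window, so this cannot be excluded, but nothing states it. If it were so, and variances were equal, the change-score figures would apply: at r = 0.7 and 8 v 4 the gain would be 48 to 50%, not 32 to 50%. With the same D-1 value as covariate, ANCOVA gives the same treatment estimate whether or not AUC is first corrected, so the recommendation does not change.

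Third, r is unknown. This stands. If entry cuts off the lower half of baseline ammonia, an r of 0.5 falls to 0.33 and the gain is 1 to 2 points at most; below break-even ANCOVA loses slightly. The truncation model is itself approximate, because it acts on the D-1 value while eligibility is judged at screening.

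Finally, baseline adjustment for asterixis is only one of two options, the drift illustration rests on an assumed shift, and NCT-A and DST changes already use baseline. All three are fair, and none carries the main point.

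**Conclusion.** The concern holds as a minor precision point. The AUC comparison leaves out a baseline value that the trial collects. The gain depends on r: nothing, or a loss of 2 to 3 points of power, below about 0.24 (8 v 12) or 0.33 (8 v 4); roughly 5 to 9 points at r = 0.5; and 18 to 25 points at r = 0.7. These figures assume a 1-SD effect, two-sided 0.05, normal data and separate two-group models, and the 8 v 12 figures also assume no drift between dose groups. The values of r here are those among enrolled patients, after any reduction from the entry limit.

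Comparisons across dose groups are the one place where adjustment may also limit bias, since randomization does not protect them against drift. The size of any such bias is unknown. The NCT-A and DST part is weaker: a gain at low to moderate r, about none near 0.8, and a small loss above that in the smaller comparison.

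**What to change.** Compare ammonia AUC between groups by ANCOVA with D-1 fasting ammonia as covariate, and keep the planned t-test or rank-sum test as a sensitivity analysis. Define the AUC window and sampling times alongside, because including the D-1 value in the AUC would make baseline part of the outcome. If ammonia is skewed, log-transform AUC and baseline first, or use a permutation test of the ANCOVA contrast.

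Secondary: compare NCT-A and DST at D7 and D15 by ANCOVA with the baseline scaled score as covariate, as is planned for quality of life.

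Wording: name baseline as the covariate for fasting ammonia, state whether placebo is pooled, and correct D5 to D15.

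**Cost.** No new data and one degree of freedom per model. The downside is up to 2 to 3 points of power for AUC if r is low, and about 3 points for NCT-A and DST at r = 0.9 (8 v 4). If the data are still blinded, only SAP wording changes. Parts of the synopsis and of Statistical methods are in the past tense; if the data are already unblinded, label the ANCOVA post hoc and report it beside the planned test.
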